Temple injections have rarely been associated with visual disturbances and blindness. Most of these have been reported with the use of fat or with HA treated in the glabellar or nasolabial fold area. Yanyuan et al.^{xiii} reported 13 cases of visual disturbance in Beijing China after facial filler injections; 4 of these were treated in the temple area with fat injections and none were treated with HA in the temple area. Park et al.^{xiv} reported 12 patients that developed retinal artery occlusion after facial filler injections; 4 of these were treated with HA, but none in the temple. (The glabella and nasolabial folds were treated). Lazzeri et al.^{xv} reviewed twenty- nine articles that described 32 patients that developed blindness after facial injections. Only 2 of these were treated with HA and neither was treated in the temple (The glabella, cheek and nasal tip were treated.) In all reports, eye pain occurred immediately after injection and was often accompanied by dizziness and nausea. Blindness has been reported to the FDA as an adverse event to HA fillers injected near the eye.^{xvi} For this reason, patients will be closely monitored post injection and visual assessments will be conducted at baseline and at the end of each injection visit using the “Vision Test” application on the iPad.

These unanticipated AEs will be reported to the FDA and IRB no later than 10 working days after the UADE onset.

If any of these UADE events occur, enrollment of this trial will be halted immediately. The patient will be sent to Bascom Palmer Eye Institute for Evaluation.

- Blindness
- Loss of visual field noted on exam by PI

Loss of Visual Acuity confirmed by iPad app or Snellen Visual Chart Mitigation of Risk

When reviewing the literature about visual disturbances caused by facial injections, it appears that the highest risk areas are injections of the glabella and nasolabial fold areas, which will not be treated in this study. Loss of visual acuity from injections in the temporal area likely occurs from retrograde embolism of ophthalmic arterial system. Multiple authors^{xvii} have discussed the ways of preventing retrograde embolism and mitigating the risk of visual disturbances and they include:

- 1) Aspiration prior to injection
- 2) Injecting slowly and with minimal pressure
- 3) Stop injection if resistance is felt
- 4) Fractionated incremental injections avoiding bolus injections
- 5) Limited total volume of substance injected

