Have a history of migraines or frequent headaches, as determined by the PI.
Have blindness or partial vision loss in either eye.
Have received any other therapy, which, in the opinion of the investigator, could interfere with safety or efficacy evaluations.
Current enrollment in an investigational drug or device study or participation in such a study within 30 days of entry into this study.
Patient who has a condition or is in a situation that, in the investigator's opinion, may put the patient at significant risk, or may significantly interfere with the patient's participation in the study.
Have received anti-coagulation, anti-platelet, or thrombolytic medications (e.g., warfarin), anti-inflammatory drugs (NSAIDs, e.g., aspirin, ibuprofen), or other substances known to increase coagulation time from 10 days pre- to 3 days post injection. A wash out period of 10 days is allowed.
Have undergone immunosuppressive therapy, chemotherapy, biologics or systemic corticosteroids within 3 months prior to each study visit.

DRUG DISPENSING

A total of 30 subjects will be treated with JUVÉDERM VOLUMA™ XC.

The JUVÉDERM VOLUMA™ XC study products will be placed in a locked temperature monitored study cabinet for the duration of the trial. On treatment day, Baseline/Visit 1, subjects will receive a treatment of a maximum of 4 total, 1 mL syringes of JUVÉDERM VOLUMA™ XC. Maximum drug allotted per subject including initial treatment and touch up treatment will be 6, 1 mL syringes.

SCREENING/ VISIT 0

Before enrollment into the study, subjects must sign the informed consent form and the HIPAA form. Once the subject has signed the informed consent and HIPAA, the following procedures will be conducted:

- Inclusion and exclusion criteria will be reviewed.
- Demographic information will be recorded.
- Medical/surgical history and concomitant medications will be obtained from the subject and recorded.
- Physical exam will be performed including vital signs and visual assessments
- The investigator will rate the subject's facial temporal areas using a scale with photo guide as follows (1 = Convexity, 2 = Flat, 3 = Mild Concavity, 4 = Moderate Concavity, and 5 =Severe Concavity). This scale will be referred to as the Frontal Temporal Fossa Rating Scale.
- Inclusion and exclusion criteria will be reconfirmed
- Subjects who do not meet the inclusion and exclusion criteria will be marked as screen failures

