- Enrolled subjects will continue with the baseline visit or enter a washout period for 10 days if needed (ex. use of anticoagulants) and then continue to baseline visit.

VISIT 1/DAY 0/ Baseline

Subjects who meet the criteria to enter into the study and who score a 3, 4, or 5 on the Temporal Fossa Rating by the investigator's assessments qualify for injection. Subjects may have the baseline visit the same day as the screening visit.

- If the baseline visit is a different day than screening visit, investigator will again review inclusion and exclusion criteria to ensure that subject is still eligible.
- Baseline photos using the Canfield VISIA Camera System will be taken.
- A urine pregnancy test will be completed for women of childbearing potential.
- Subject will complete their self-assessments.
- The subject will be administered the "Vision Test" on the iPad.
- If the subject qualifies for injection, the following procedures will also be conducted.
- Subjects will receive up to 4, 1 mL syringes of JUVÉDERM VOLUMA™ XC, by the Treating Investigator.
 - Subjects may receive ice packs to reduce swelling and bruising post-treatment. Any actions taken will be documented.
 - Monitor treatment subject for at least 15 minutes post injection.

- Post injection, the subject will be again be administered the “Vision Test” on the iPad
- Physical exam will include a visual field analysis assessed as follows:
 - The examiner should be nose to nose with the patient, separated by approximately 8 to 12 inches.
 - Each eye is checked separately. The examiner closes one eye and the patient closes the one opposite. The open eyes should then be staring directly at one another.
 - The examiner should move their hand out towards the periphery of his/her visual field on the side where the eyes are open. The finger should be equidistant from both persons.
 - The examiner should then move the wiggling finger in towards them, along an imaginary line drawn between the two persons. The patient and examiner should detect the finger at more or less the same time.
 - The finger is then moved out to the diagonal corners of the field and moved inwards from each of these directions. Testing is then done starting at a point in front of the closed eyes. The wiggling finger is moved towards the open eyes.
 - The other eye is then tested

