- A diary will be dispensed for subjects to record any reaction to study product or comments prior to Visit 2. Subjects will be instructed on diary completion
- The treating investigator will review the Vision Test results, compare to baseline and examine the patient prior to dismissal.
- Subjects will be instructed to contact the office if they experience any unexpected side effects including intense pain of the skin, eye pain, or visual disturbances. In case of an emergency, subjects will be instructed to call 911.

DAY 3 POST INITIAL TREATMENT FOLLOW UP PHONE CALL (±1 DAY)

- Subjects who received treatment will be called and questioned about AEs, SAEs, changes in concomitant medications, or concomitant procedures.
- Subjects will be reminded to complete study diary and call the office if any issues may arise.
- Subjects will be reminded of exclusionary concomitant medications/procedures.

VISIT 2/WEEK 2 FOLLOW UP/ POSSIBLE TOUCH UP/ (±3 DAYS)

Treated subjects will come for a follow up at week 2 (±3 days) after initial injection. The following procedures will be conducted:

- Study diary will be collected and reviewed.
- Changes in adverse events and concomitant medications/procedures will be documented.
- Subject’s vitals and weight will be documented.
- The Vision Test will be administered on the iPad.

- Physical exam will include a visual field analysis
- Photos using the Canfield VISIA camera will be taken.
- Treatment subjects will complete the assessments.
- If Treating Investigator determines a touch-up is indicated, then perform the following:
 - Subjects' vital signs will be taken
 - Touch up will be performed by the treating investigator. The combined initial treatment and touch up treatment drug total per subject will not exceed 6cc (six 1 mL syringes) of JUVÉDERM VOLUMA™ XC.
- Subjects may receive ice packs to reduce swelling and bruising post-treatment. Any actions taken will be documented.
- Monitor treatment subject for at least 15 minutes post injection.
- The Treating Investigator will review the Vision Test results, visual field exam and compare to baseline results and examine the patient prior to dismissal.
- A diary will be dispensed to subjects to record any reaction to study product or comments for collection at the month 1 visit.

Subjects will be scheduled for the next visit and reminded to complete their diaries and return them at the next visit

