If subjects report any unexpected side effects at this visit or at any time after injection, they will be scheduled to come to the office for evaluation.

DAY 3 POST TOUCH-UP TREATMENT FOLLOW UP PHONE CALL (±1 DAY)

- Subjects will be called and questioned about AEs, SAEs, changes in concomitant medications, or concomitant procedures.
- Subjects will be reminded to complete study diary and call the office if any issues may arise.
- Subjects will be reminded of exclusionary concomitant medications and procedures.

VISIT3 /MONTH 1(±7 DAYS)

At this visit(s), the following procedures will be conducted:

- Changes in adverse events and concomitant medications will be documented.
- Subject's vitals and weight will be documented.
- Photos using the VISIA will be taken.
- Subject will complete the following assessments:
 - Subject's Satisfaction with Temple Appearance
 - Subject Self-Perception of Age
- Treating investigator will rate the subject's treatment area using the Temporal Fossa Rating Scale, Investigator's Satisfaction with the Appearance of the Temporal Regions, and the Subject Global Aesthetic Improvement Scale (GAIS)
- Subjects will be scheduled for next visit.

- Subjects will be scheduled for next visit.

VISITS 4,5,6 /MONTH 3,6,and 9 (±7 DAYS)

At this visit, the following procedures will be conducted:

- Changes in adverse events and concomitant medications will be documented.
- Subject's vitals and weight will be documented.
- Photos using the VISIA will be taken.
- Subject will complete the following assessments:
 - Subject's Satisfaction with Temple Appearance
 - Subject Self-Perception of Age
- Treating investigator will rate the subject's treatment area using the Temporal Fossa Rating Scale, Investigator's Satisfaction with the Appearance of the Temporal Regions, and the Subject Global Aesthetic Improvement Scale (GAIS)
- Subjects will be scheduled for next visit.

If subjects report any unexpected side effects at these visits or at any time after injection, they will be scheduled to come to the office for evaluation.

VISIT 7/MONTH 12- STUDY EXIT (±7 DAYS)

At this visit, the following procedures will be conducted:

- Changes in adverse events and concomitant medications will be documented.
- Subject's vitals and weight will be documented.
- Photos using the VISIA will be taken.
- Subject will complete the following assessments:
 - Subject's Satisfaction with Temple Appearance
 - Subject Self-Perception of Age

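### No objective vision test is scheduled after Week 2, so a visual deficit appearing after the day of a touch-up would be found only through symptom or adverse event report

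*Combined protocol and SAP*

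**What the plan says.** The UADE section sets the policy: "patients will be closely monitored post injection and visual assessments will be conducted at baseline and at the end of each injection visit". It lists three events that halt enrollment and require reporting. Besides blindness, these are field loss found by the investigator on examination, and "Loss of Visual Acuity confirmed by iPad app or Snellen Visual Chart".

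The visit sections carry this out as follows.

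- Screening: "Physical exam will be performed including vital signs and visual assessments", without naming which visual assessments.
- Visit 1: the Vision Test is listed before injection and again after it. The field exam appears after the second test: "Physical exam will include a visual field analysis assessed as follows".
- Visit 2: "Treated subjects will come for a follow up at week 2 (±3 days) after initial injection". For all treated subjects, "The Vision Test will be administered on the iPad" and a field exam is done. Both items precede the touch-up step.
- Month 1, Months 3, 6 and 9, and Month 12: adverse events, concomitant medications, photographs and aesthetic scales are listed, and the subject's "vitals and weight will be documented". No Vision Test or field exam appears.

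The Vision Assessments section expects filler harm to show more often as a field defect than as a change in acuity.

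**The concern.** Visual harm is the gravest risk the protocol discusses, and safety is part of the stated primary endpoint. The two injection sessions are not followed alike. The first has a same-day check and an objective recheck about two weeks later. The second, after which cumulative volume is at its highest (up to 6 syringes against up to 4), has no scheduled check after the day itself.

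What is at stake is what the study can report. For re-injected subjects it could say that nobody reported a later visual problem. It could not say that acuity and fields were measured and found unchanged. Field loss is the deficit the plan thinks more likely, and it is the one the symptom tools cover least.

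**Working it through.** The plan states no figure to reproduce. The check compares the visit lists and does day arithmetic, with Day 0 as the first injection. Assumptions: Month 1 is 28 to 30 days counted from Day 0, Month 6 is 183 days and Month 12 is 365 days.

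**1. Visits with a listed vision check.** Visits 0, 1 and 2, so 3 of 8. After Week 2 the count is 0 of 5 (Visits 3 to 7).

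**2. Last scheduled objective test.** Week 2 ±3 days: 14 − 3 = Day 11 and 14 + 3 = Day 17.

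**3. Follow-up without a scheduled test.** With exit at Month 12: 365 − 17 = 348 days, and 348/365 = 95%. The Design section allows exit at Month 6 instead: 183 − 17 = 166 days, and 166/183 = 91%. The finding does not depend on which exit date is right.

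**4. Where Month 1 falls after a touch-up.** The window is 28 ± 7 = Day 21 to 35, or 30 ± 7 = Day 23 to 37. The shortest gap from touch-up is 21 − 17 = 4 days and the longest is 37 − 11 = 26 days. It is the first visit after a touch-up and the nearest match to the Week 2 recheck.

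**5. What still collects visual symptoms after a touch-up.**

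| Source | Timing | Vision content |
|---|---|---|
| Day 3 call (±1), Appendix G | Day 11 + 2 = 13 to Day 17 + 4 = 21 | Eye pain; blurred or decreased vision |
| Second 14-day diary, Appendix F | Ends Day 11 + 14 = 25 to Day 17 + 14 = 31 | Eye pain, blurred vision, decreased vision |
| Adverse event query | Every visit to exit | Subject report and investigator observation |
| Office evaluation | Any time, if the subject reports something | Content not specified |

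The diary and call script each have a free "other" row but no field-loss item. The Visit 2 list says the second diary will be collected at Month 1, yet the Month 1 list has no collection or review step.

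**6. Same-day check at the touch-up.** The Visit 2 list itemises no test after the touch-up. The UADE policy, and the Design statement that a touch-up follows the procedures of the first injection visit, imply one. Hence a same-day check at most.

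**7. What a clean result would mean.** If all 30 subjects were re-injected and none reported a late deficit, the exact one-sided 95% upper limit would be 1 − 0.05^(1/30) = 9.5%. That limit applies to the true rate only if symptom and adverse event report finds every late deficit. With fewer re-injected subjects the limit is higher.

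**The case against.** The strongest reply is that the plan does what it promises. It commits to testing at baseline and at injection visits, and Visits 3 to 7 are not injection visits. That stands: a reader might infer that the lists contradict the UADE section, and they do not.

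A reader might also infer that visual outcome goes unmeasured after Day 17. The documents do not support this. Symptoms are solicited by call and diary, adverse events are recorded to exit, and a reported problem leads to an evaluation. Only scheduled objective testing is missing.

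Nor do the two exam-based halt events become inoperable. Either can be established at an unscheduled evaluation, though only after the subject has reported something.

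It is also tempting to say that the protocol deliberately chose a two-week recheck after the first injection. No section says so. Visit 2 is the possible touch-up visit, and its tests fit equally well as checks before a second injection. The unequal follow-up is a fact; the motive is unknown.

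Finally, the protocol says that in all published reports eye pain was immediate, and gives embolism as the likely mechanism. This supports the same-day focus and lowers the expected yield of later testing, most of all at Month 12. It does not remove the point. Those reports concern patients recognised because they had visual disturbance or loss, so they say little about smaller deficits. That a subject might fail to notice a field defect is my inference, not a statement in the documents.

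**Conclusion.** The point holds as a gap in safety ascertainment. No acuity or field test is scheduled after Week 2 (Day 17 at the latest), and after a touch-up any later deficit is found only by symptom or adverse event report.

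The number affected is the number re-injected. This may be anywhere from 0 to 30, because the touch-up is at the investigator's discretion. The number of deficits that would be missed cannot be estimated from the documents and may well be small. The conclusion rests on reading the visit lists as complete and on counting Month 1 from the first injection. If Month 1 were counted from the touch-up, its window would fall 21 to 37 days after it, still with no vision test.

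This is a worthwhile, inexpensive improvement rather than a flaw that invalidates the study. The case is strongest for Month 1 in re-injected subjects and weak for the exit visit.

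**What to change.** 1. Add the Vision Test and visual field exam to the Month 1 list as safety outcome assessments, at least for subjects injected at Visit 2.
2. Compare acuity with the Vision Test done before injection at Visit 1.
3. List the field exam explicitly before injection at Visit 1. It is now itemised there only after the post-injection test, and screening does not name it, so no explicit pre-injection field result exists.
4. Report acuity and field change from baseline at Week 2 and Month 1.
5. Add collection and review of the second diary to the Month 1 list, to match the Visit 2 instruction.

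An exit-visit test is optional. Its yield is likely to be low, and a late change in a single-arm study is hard to attribute to the product.

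The cost is a few minutes per subject at existing visits, using the app and bedside exam already on site. The real downside is chance change on the app. The acuity event in the UADE section states no threshold and halts enrollment, so an isolated change should be confirmed by a repeat test, and the sponsor should state how a repeat result bears on that event. I propose no threshold.

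Two related passages need reconciling: whether a vision test follows the touch-up at Visit 2, and whether subjects exit at Month 6 or Month 12.

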Subjects will return two weeks post initial injection for a possible touch up. The treating investigator will determine whether a touch up treatment is necessary. Prior to treatment, subject diaries will be collected and reviewed. All AEs/SAEs, changes in concomitant medications and concomitant procedures will be documented. Per the treating investigator's discretion, the subject may or may not qualify for a touch up. The subject will undergo photos. If treatment is necessary, subject will undergo same procedures as the initial injection visit. Post-treatment photos will be taken and subject will receive another diary and 3 day post injection phone call.

Follow up visits will consist of documentation of AEs/SAEs, changes in concomitant medications and changes in concomitant procedures at the beginning of the visit. The investigator and subject will complete their respective assessments and photos will be taken.

ENDPOINTS

The primary endpoint of this study is to determine the efficacy and safety of JUVÉDERM VOLUMA™ XC when used in the facial temporal regions based on the change in the score of the investigator's Temporal Fossa Scale. The secondary endpoints are the 2-point change in the scale of Subject's Satisfaction of Facial Appearance and Investigator's Satisfaction Scale.

STUDY PROCEDURES

PROCESS OF CONSENT/SUBJECT COMPREHENSION

All subjects will first be given the informed consent to read over by themselves. One of the investigators and a qualified member of the research staff will then review the informed consent with the prospective subject. The subject will then be allowed ample time to ask any questions about the study, and all questions will be answered. The person obtaining consent will ensure that the subject has a clear understanding of the study procedures. Once all questions are answered and the subject chooses to enroll in the study, the subject will be asked to sign the IRB-approved informed consent document. No study procedures will be conducted prior to signing the informed consent. Each subject will receive a copy of their signed informed consent for their information.

CONSENT FORMS

IRB approval will be obtained prior to use of the consent form.

INCLUSION CRITERIA

Subjects must meet the following inclusion criteria to be enrolled in this study:

Be willing and able to read and sign the informed consent and other study documents.

Male or female, 35- 75 years old.

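### The Visit 2 list omits the vision reading after the touch-up that the UADE and Design sections call for, and nothing requires acuity to be checked against baseline before the second injection

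*Combined protocol and SAP*

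**What the plan says.** The UADE section names three events that stop enrollment at once: blindness, loss of visual field on the investigator's examination, and "Loss of Visual Acuity confirmed by iPad app or Snellen Visual Chart". It also sets the timing of the readings: "visual assessments will be conducted at baseline and at the end of each injection visit", using the iPad application.

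The Design section says of the touch-up: "If treatment is necessary, subject will undergo same procedures as the initial injection visit". The sentence that follows names photographs, a diary and a phone call, but not vision testing.

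The Visit 1 list has a Vision Test before the injection and a second one after it ("Post injection, the subject will be again be administered the" iPad test), followed by a visual field exam and a review against baseline before the subject leaves.

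The Visit 2 list says once, above the touch-up step, "The Vision Test will be administered on the iPad", and adds a visual field exam. Next comes the conditional step, "Touch up will be performed by the treating investigator", then ice packs and at least 15 minutes of monitoring. Only then does it say: "The Treating Investigator will review the Vision Test results, visual field exam and compare to baseline results and examine the patient prior to dismissal".

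**The concern.** The acuity trigger works only if there is a reading taken after the injection that might have caused the loss. At Visit 1 there is one. At Visit 2 the listed reading comes before the touch-up, so the review against baseline at the end of the visit would use a value that the touch-up could not have affected.

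A second gap sits beside it. The week-2 acuity reading could show a loss left by the first session, but it is listed for review only after more filler has been given. The one review that the Design section places ahead of the touch-up is of the diaries.

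At stake is a loss that the subject does not notice. It could go unmeasured after the second injection or, for acuity, go unrecognized until after that injection.

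**Working it through.** The plan states no figure to reproduce. The check sets the two injection-visit lists side by side and compares them with the general rules.

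| Step | Visit 1 list | Visit 2 list |
|---|---|---|
| Vision Test before injection | listed | listed once |
| Vision Test after injection | listed | not listed |
| Field exam before injection | not listed at this visit (Screening lists visual assessments) | listed once |
| Field exam after injection | listed | not listed |
| Monitoring of at least 15 minutes | listed | listed |
| Review against baseline before the subject leaves | Vision Test | Vision Test and field exam, placed after the touch-up |

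**Post-injection acuity readings per injection visit.** The UADE section requires 1. The Visit 1 list supplies 1. The Visit 2 list supplies 0.

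**What the listed readings can show.** Call the baseline reading A and the single Visit 2 reading B. If B is taken before the touch-up, B against A can show loss from the first session but not from the second. If the bullets are not a strict sequence and B is taken afterwards, B can show loss from the touch-up, but nothing is left to clear the subject for it. One reading cannot do both, so the omission does not depend on bullet order.

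**Field exam.** The Visit 1 list describes a confrontation test, in which subject and examiner should see the finger at about the same moment. A defect shows while the test is done. The gap before the touch-up is therefore about acuity. The gap after the touch-up applies to both tests.

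**How many sessions.** There are 30 first sessions and t touch-ups, at most one per subject. The plan does not give t: the Design section says in one place that subjects will have a touch-up and in another that the investigator decides. Over an assumed range, the share of injection sessions with no post-injection reading in the visit list is t/(30 + t):

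- t = 10: 10/40 = 25%
- t = 20: 20/50 = 40%
- t = 30: 30/60 = 50%

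These shares apply only if staff work from the visit list alone. If they apply the UADE and Design sections, the share without a post-injection acuity reading is 0%.

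**The case against.** The strongest reply is that the protocol already requires the reading. The UADE section asks for it at every injection visit, and the Design section carries the Visit 1 procedures over to the touch-up. This stands. A reader might infer from the Visit 2 list that the protocol has no vision reading after the touch-up at all, and the documents do not support that. What remains is a conflict between sections. The list staff follow on the day omits the step, and the Design cross-reference is general and does not mention vision. Neither provision requires a comparison with baseline before the touch-up.

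A second reply is that a vascular event would announce itself. The protocol says that eye pain came on immediately in all the reports it reviews. After a touch-up there are at least 15 minutes of monitoring, an examination whose content is not specified, a diary and a day-3 call that both ask about eye pain and vision, and office evaluation of unexpected effects at any time. This also stands, and it limits the point to unnoticed loss. No document describes a silent case after filler.

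Two further readings are tempting but fail:

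- The follow-up lists from Month 1 to Month 12 name no vision test, which a reader might count as part of the gap. No injection is given at those visits and the plan promises no test there.
- A reader might argue that measuring touch-up sessions would tighten a safety limit. Two sessions in one person are not independent, the plan makes no per-session claim, and per subject the denominator stays at 30 either way.

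**Conclusion.** The point holds as an inconsistency with a safety consequence. The Visit 2 list lacks the post-touch-up reading that two other sections call for, and no section requires the week-2 acuity reading to be compared with baseline before the second injection.

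It affects at most 30 touch-up sessions. The number of losses that would be missed cannot be estimated from the documents and is probably small, because most events would cause symptoms. The conclusion assumes that staff work mainly from the visit list; staff who apply the UADE and Design sections would retest.

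It should be corrected because the remedy is cheap and the acuity trigger halts enrollment. It does not show that vision after the touch-up is unmonitored.

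**What to change.** Change the Visit 2 list in two places.

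1. Before the touch-up, review the Vision Test against baseline and review the field exam result. If acuity is worse or a field defect is found, follow the existing UADE steps and do not inject.
2. Within the touch-up step, after the 15-minute monitoring, repeat the Vision Test and the field exam and compare the new readings with baseline before the subject leaves. The UADE section already requires the acuity reading. The field exam follows from the Design section, since the Visit 1 list places one after injection. For the field exam, the only reference listed before any injection is the visual assessment at Screening.

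Leave the three triggers, the enrollment halt and the eye-institute evaluation unchanged.

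The cost is a few lines of text and one extra Vision Test and field exam per touch-up, a few minutes each, for at most 30 subjects (60 eyes), with no new equipment. The downside is that a chance worse reading could postpone a touch-up, possibly beyond the 3-day window, or set off the existing halt, because the plan gives no size of drop that counts as loss. A worse acuity reading should therefore be repeated at once in the same eye, with the same method as at baseline. The repeat documents the finding and does not cancel the examination or the evaluation.
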